5.5. Description of Study Processes

5.5.1. Instrument Administration

A study staff member will administer study assessments at baseline and multiple follow-up time points (see Table 1) within a +/- 2-week window to accommodate patient schedules. The assessment battery takes approximately 20 minutes to complete. Patients may complete assessments either in the clinic, online via REDCap email, on paper at home, via telephone, or via institution-approved video technology. As a first preference, we will attempt to collect questionnaires in-person at scheduled visits to the outpatient

clinic. We will ask patients to provide their email address to allow us to email study measures using a secure electronic system when patients do not have a clinic appointment within the follow-up time points. For patients who opt out of using email, we will either send them paper copies of the survey or ask them to complete them verbally over the telephone or via institution-approved video technology. Surveys that are completed on paper at home will be labeled only with a case number and no identifying information; we will also add a note reminding participants to please not add their name or identifying information to the survey. We will provide a pre-paid, stamped envelope for participants who want to return questionnaires by mail.

Spanish speaking participants will have the option of completing follow-up assessments in-person as a first preference, or otherwise via mail. Study staff who are fluent in Spanish may administer questionnaires via telephone or via institution-approved video technology. Spanish questionnaires will not be administered via email as this is not possible with REDCap.

We will administer patient-reported measures for 48 weeks from enrollment. We selected a longer administration period in the current study as the median survival for patients with lung cancer is now approximately one year. The selected self-report measures have strong psychometric properties and have been well validated in previous studies. All study measures are available in both English and Spanish, except the Prognosis and Treatment Perceptions Questionnaire, which were translated (forward and backward) into Spanish with a native Spanish speaking clinician.

5.5.2. PC Intervention Administration

All participating PC clinicians will undergo training to ensure that the provision of PC services is consistent across study sites. Drs. [name] and [name] developed a PC intervention guide based upon our prior studies that details the elements of PC in the outpatient care setting.⁶⁰⁻⁶² The intervention guide outlines the domains that the PC clinicians will address at the initial visits (e.g., establishing a therapeutic relationship), visits throughout the disease course (e.g., symptom management and coping), and visits at the EOL (e.g., EOL care options), highlighting the essential elements and key points of each care domain. The delivery of PC in both study arms will follow the intervention guide, with only the frequency and timing in which patients engage with PC differing by study arm. We also developed a series of training videos to illustrate the techniques included in the guide. Both the intervention guide and training videos are being used in our ongoing Alliance for Clinical Trials multi-site PC trial. Prior to the study start, all participating PC clinicians will watch the training videos. They will then attend a four-hour training using video conferencing to review the intervention guide (the site PIs will complete this during their in-person or virtual training), led by the MGH study staff. They will also lead monthly supervision calls with the participating PC clinicians throughout the trial and ensure that new PC clinicians will receive training. Table 2 below summarizes the domains, elements, and key points of the PC intervention visits.

Table 2. Palliative care visit summary

Timing	Domain	Elements	Key Points
--------	--------	----------	------------

Initial Visits	Therapeutic Relationship	
 • Introducing PC • Understanding the Patient and Caregiver Experience • Building Trust with the Patient and Caregiver 	
 • Develop a strong therapeutic relationship with patients and caregivers • Learn about the values, life goals, and experiences of patients and their caregivers both prior to and after the cancer diagnosis • Develop trust and credibility with patients and caregivers by providing reassurance and outlining parameters of communication
All visits	Patient Symptoms	
 • Preparing for Symptoms • Assessing & Treating Symptoms • Coordinating Symptom Management with Oncology • Providing Referral for Symptom Management 	
 • Clarify the symptoms the patient will likely experience and offer reassurance about the methods for reporting and treating symptoms • At every visit, elicit existing and new symptom concerns • Maintain ongoing, effective communication with oncologists to define mutual collaboration and work within their preferred practice patterns • Emphasize team approach to care by referring to specialty care, mental health, alternative medicine, and spiritual support as needed
	Coping with Advanced Cancer	
 • Reviewing & Validating Prior Coping Efforts • Discussing & Advocating for Different Methods of Coping • Supporting Caregiver Coping • Providing Referral for Additional Support 	
 • Recognize that patients and caregivers bring their own expertise in coping to the current circumstance based on prior experiences • Introduce strategies to help improve adjustment and meaning in life (e.g., behavioral, cognitive, and spiritual approaches; social support) • Bolster caregiver coping by assessing burden, enhancing their communication with patients, and recommending additional support • Involve other members of the team for patients and caregivers who may be experiencing severe distress (e.g., social work, psychology)
	Prognostic Awareness & Illness Understanding	
 • Communicating with Oncology • Exploring Goals & Values • Assessing & Informing Patient Expectation of Prognosis • Conducting Separate Conversations with Caregivers 	
 • Consult with the oncologist to ensure the care team is consistent with their understanding of the patient's prognosis • Assess patient's hopes and expectations for treatment and future to clarify the patient's level of prognostic awareness • Recognize that illness understanding often vacillates between more & less realistic expectations and work to improve prognostic awareness • Include both patients and caregivers in conversations about prognosis and illness understanding when possible
	Treatment Decision-making	
 • Assessing Patient Values in Treatment Decision-Making • Discussing Treatment Considerations • Supporting Treatment Decisions 	
 • Elicit information from patients and caregivers regarding their decision-making style, quality versus quantity of life concerns, and life goals • Provide support for patients and caregivers to understand the efficacy, and risks and benefits associated with cancer treatment • Clarify any misunderstanding about treatment, support patient decision-making and freedom to change course
Visits Near EOL	EOL Care	
 • Discussing EOL Care Options • Supporting Caregivers in EOL Care Coordination & Bereavement 	
 • Discuss/review selection of healthcare proxy, determination of resuscitation preferences, transition to hospice care, and location of death • Determine available resources for EOL care and whether it is appropriate for patients to receive care in the home or other settings; and provide resources and counseling for bereavement for caregivers

5.5.3. Ensuring Fidelity of Study Design, Training, and Intervention

We will take several steps to ensure the fidelity of our study design, training, and intervention delivery. Specifically, for the study design, we will utilize an evidence-based PC intervention guide, measure the number and duration of PC visits, and monitor the proportion of stepped care patients who transition to step 2 of the intervention. Also, we will employ rigorous training procedures for site PIs and study staff; use of video to illustrate delivery of the PC intervention; video-conferencing for training site PC clinicians and training for new PC clinicians; and monthly calls with the PC clinicians (led by [name]) and the study staff (led by the MGH Project Manager). To ensure the

fidelity of intervention delivery, we will review PC documentation, and provide feedback to PC clinicians. As noted previously, the participating PC clinicians will complete an electronic survey after each clinical encounter to record the topics addressed during each visit. Two study staff will independently review the electronic surveys every 3 months to ensure intervention fidelity and conformity between sites in addressing the domains and topics as specified by the guide, allowing assessment of inter-rater agreement. Coder disagreement will be resolved via consensus discussion with [name]. Based on this review, [name] will provide constructive feedback as needed to individual clinicians to confirm fidelity to the PC intervention. Trained study staff will also review PC notes in the health record to ensure adherence to the intervention guide content and provide feedback to clinicians at the site research meetings.

5.5.4. Special Concerns

Study staff at MGH, Duke, and Penn will all meet on a weekly basis to discuss any issues or concerns with study procedures. If it is decided that the protocol needs to be amended or modified, the lead site PI will make the necessary changes and submit an amendment to the DF/HCC IRB for approval. Once the amendment has been approved by the DF/HCC IRB, then the amendment will be submitted to the Duke IRB and the Penn IRB.

5.6. Adverse Reactions and their Management

5.6.1. Reporting Adverse or Unanticipated Events

Identification of adverse events may come through notification from the study participant, caregiver, clinician, or from review of the EHR. In such circumstances, the PIs and investigative team will follow the following procedures:

Serious Adverse Events: Given that this study is a PC intervention, we do not anticipate any study-related events meeting the FDA definition of a SAE (i.e., any fatal event, immediately life-threatening event, permanently or substantially disabling event, event requiring or prolonging inpatient hospitalization, or any congenital anomaly). This study population is comprised of individuals diagnosed with advanced lung cancer who frequently experience disease worsening, high rate of symptoms, and hospitalizations from the underlying disease and/or side effects of treatment. Therefore, as advanced lung cancer is a chronic-type terminal illness, regular fluctuations in cancer-related symptoms, disease worsening, hospitalizations, emergency department visits, and deaths are to be expected throughout the study, and we will not consider or report such events as SAEs in this trial.

Non-Serious Adverse Events: The IRB will be provided with unblinded summaries of study related non-serious adverse events by treatment group at the continuing reviews. These reports will include types of events, severity, and treatment phase. To date, we have had very few non-serious events in our supportive care studies.

5.6.2. Anticipated Reactions

As this is a behavioral study, there are no ingested medications, and no biomedical procedures. It is unlikely that participants will be at any risk for physical harm as a result of study participation.

Participants may find some of the questions asked in the questionnaire to be emotionally upsetting and may experience some fatigue from the length of the assessment battery. As this is a study targeting symptoms that are debilitating and interfere with QOL, it is possible that some participants will experience depression.

5.6.3. Reaction Management

A detailed consent form will be signed by each participant following the explanations by the study staff or oncology clinician. The consent form will include all study procedures, information about potential risks and benefits of participation, and information regarding whom the participant can contact for further questions. It also will state that participation is voluntary, that participants can refuse to answer any question, that they can withdraw from the study at any time, and that study participation is in no way related to their medical care. All study staff will complete the required human subjects training before working on any human subject aspects of the study.

Should a participant exhibit or express distress, they will be reassured by the study staff that they need not answer any questions they find upsetting. They will also be reminded that study participation is voluntary. If participants remain distressed, both the PI and the primary oncology clinician will be notified. Should several participants express distress over an individual item, the study staff will review the questionnaire and contact the IRB to consider removing it from the study.

If a participant reports severe distress or suicidal ideation during the study conduct, the study staff member has an obligation to inform the site PI and/or a member of the patient's PC or oncology team. These clinicians will determine the need to involve psychiatry and take further action as deemed necessary. The study staff will review sensitive items regarding suicidal ideation within 120 hours (5 business days) of receipt of completed surveys and will report any suicidal ideation to the site PI and/or a member of the patient's PC or oncology team promptly.

6.0. Ethical and Legal Issues

6.1. Confidentiality

Patient data will be collected at each institution (MGH, Duke, and Penn) using REDCap. Each site will maintain their own separate list of patient names and study ID's, which will be saved in secure electronic files. Participants will be identified on study forms by case number only to protect confidentiality. Identifiers such as name will only be used during the initial data retrieval process and can be destroyed once all data records have been obtained and data analysis has been completed as discussed previously. At the completion of the study, de-identified data files will be transferred from Duke and Penn to the MGH using a secure data transfer.

Participants' responses to survey questions will remain confidential unless there is active suicidal ideation confirmed by the study staff. Under these circumstances, as clearly stated in the patient consent form, the study staff member will inform the patient's site PI and/or a member of the patient's PC or oncology team. These clinicians will then

determine the need to involve social work, psychiatry and/or take further action as deemed necessary.

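### Sections 5.6.3 and 6.1 set different triggers for passing on suicidal ideation found in a survey, and the review time limit is stated in two units that do not agree

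*Protocol*

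**What the plan says.** Protocol section 5.6.3 (Reaction Management) gives the operating procedure. Its general duty reads: "If a participant reports severe distress or suicidal ideation during the study conduct, the study staff member has an obligation to inform". Those to be told are the site PI, PC or oncology clinicians, or both. For questionnaires the section adds a deadline for reviewing the relevant items, "within 120 hours (5 business days) of receipt of completed surveys". After that review, staff "will report any suicidal ideation to the site PI" or those clinicians, or both, promptly. Neither the general duty nor the survey rule is limited to active or confirmed ideation.

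Protocol section 6.1 (Confidentiality) covers the same questionnaires. Participants' "responses to survey questions will remain confidential unless there is active suicidal ideation confirmed by the study staff". In that event, "as clearly stated in the patient consent form", staff inform the site PI and/or a member of the PC or oncology team.

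Section 5.5.1 (Instrument Administration) allows surveys to be completed in clinic, by telephone or by video, but also "online via REDCap email, on paper at home".

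**The concern.** Both sections tell study staff what to do with a survey answer, and both name the same recipients, but the conditions differ. In 5.6.3 any ideation is enough. In 6.1 the ideation must be active and must have been confirmed by staff. Neither section defines active, describes how or by when confirmation is obtained, or says which section governs.

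This matters most for a survey returned online or by post. The written answer may then be the only signal, and nobody may yet have spoken to the participant. Staff who look to 6.1 would hold that answer back until confirmation, or indefinitely if the ideation is judged not active. What is at stake is the safety of an individual participant and a consistent account of confidentiality. No estimate or test in the trial depends on it.

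The double time limit is a smaller fault in the same paragraph of 5.6.3: a review can be on time in one unit and late in the other.

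**Working it through.** **Trigger.** No arithmetic applies, so the two rules are set side by side for each kind of survey answer.

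| Survey answer | Section 5.6.3 | Section 6.1 | Result |
|---|---|---|---|
| Active ideation, confirmed by staff | Report | Inform | Agree |
| Active ideation, not yet confirmed (for example, participant not reached) | Report | Keep confidential | Conflict |
| Ideation that is not active | Report | Keep confidential | Conflict |

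Reporting to the site PI alone does not reconcile the last two rows. Section 6.1 lists informing the site PI as part of its exception, so on its own terms that step also waits for active, confirmed ideation.

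**Time limit.** The inputs are the two figures in 5.6.3: 120 hours and 5 business days.

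- The plan's hour figure is 5 × 24 = 120 hours, which is five calendar days.
- Counting business days from the day after receipt, with no public holiday, a survey received on any day from Monday to Friday reaches its fifth business day on the same weekday of the next week: 7 × 24 = 168 hours.
- Difference: 168 − 120 = 48 hours. Ratio: 168 / 120 = 1.40, so 40% longer.
- A Saturday receipt gives 6 × 24 = 144 hours, and a Sunday receipt gives 5 × 24 = 120 hours. Only Sunday matches.
- If the receipt day is counted as day 1, a Monday receipt gives 4 × 24 = 96 hours, and a Tuesday to Friday receipt gives 6 × 24 = 144 hours. Neither equals 120.

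Under either counting convention, the two units disagree for every weekday receipt.

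**The case against.** The strongest reply is that 6.1 is a general privacy statement, while 5.6.3 is the procedure: it names the reviewer, the deadline, the recipients and the duty. Staff holding a positive answer would naturally turn to 5.6.3, which is also the more protective rule. Weekly cross-site meetings (5.5.4 and 9.12) and yearly case audits (9.12) make lasting differences between sites less likely. This lowers the practical risk and is a reason to call the point minor. It does not remove the conflict, because 6.1 also prescribes an action by staff, presents its condition as the only exception, and is not made subordinate to 5.6.3.

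On the time limit, one can say that the hours are shorthand and business days are the real unit, since section 5.3.1 gives five business days for scoring the FACT-L. That is plausible, but it means that the hour figure is wrong and should go.

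A reader might infer more than the documents support:

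- *That severe distress is caught in the same conflict.* Section 6.1 governs answers to survey questions. The step under which "both the PI and the primary oncology clinician will be notified" concerns a participant who stays upset after reassurance, which staff observe directly. No survey item or cutoff for severe distress is named.
- *That following 5.6.3 breaks a promise made in the consent form.* In 6.1 the reference to the consent form attaches to the duty to inform when ideation is active and confirmed. It does not say that participants were promised silence otherwise. The consent pages are not available, so this can only be a point to check.
- *That the adverse-event plan is deficient.* Section 5.6.2 notes that "it is possible that some participants will experience depression", and nothing says how an ideation answer is classified. But 5.6.1 and 9.12 set general routes for identifying and reporting events, and a protocol need not classify each questionnaire answer in advance.
- *That a known number of answers is affected.* The documents give no rate of positive answers and no share that is not active or not confirmed, so no count can be given.

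**Conclusion.** The point holds as a contradiction between two stated rules, limited to survey-reported ideation that is not active or not yet confirmed. For active, confirmed ideation the sections agree, so it would be wrong to call them opposite throughout. The time limit is inconsistent by 48 hours for a weekday receipt, assuming that days are counted from the day after receipt and no holiday intervenes.

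Severity is minor. The primary, secondary and exploratory analyses are untouched. SAP section 2 reports that 510 patients were enrolled, so an amendment can reach only the surveys that remain; the documents do not say how many. Nothing in them shows that any site withheld an answer or that sites acted differently. The conclusion rests on the text of the two sections alone.

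**What to change.** 1. In section 6.1, change the exception to any suicidal ideation reported in a survey, matching 5.6.3. State that confirming whether it is active determines how urgently clinicians act, and not whether they are told.
2. In section 5.6.3, state one review limit and delete the other. Keeping 120 hours is the simpler choice. A survey received on Monday then falls due on Saturday, which leaves Tuesday to Friday. One received on Friday falls due on Wednesday, which leaves Monday to Wednesday. Weekend cover may be needed where staffing is thin.
3. Check that the consent form carries the same rule. If it carries the narrower condition, take that difference to the IRB with the amendment.

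The cost is wording in two protocol sections, a consent-form check, and an amendment through the lead IRB and then the two other sites' IRBs, as section 5.5.4 describes. The SAP needs no change.

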7.0. Statistical Analysis

7.1. Primary Endpoint

To determine whether stepped PC is non-inferior to early integrated PC in improving patients' QOL at 24 weeks.

7.2. Secondary Endpoints

- 7.2.1. To assess whether stepped PC is non-inferior to early integrated PC with respect to patient-clinician communication about EOL care preferences.
- 7.2.2. To assess whether stepped PC is non-inferior to early integrated PC with respect to length of stay in hospice.
- 7.2.3. To compare the superiority of stepped PC versus early integrated PC with respect to resource utilization.

7.3. Exploratory Endpoints

- 7.3.1. To compare the longitudinal patterns in QOL in patients assigned to stepped PC versus early integrated PC, as measured by repeated assessments of FACT-L.
- 7.3.2. To compare the superiority of stepped PC versus early integrated PC with respect to cost-effectiveness.
- 7.3.3. To compare coping strategies in patients assigned to stepped PC versus early integrated PC.
- 7.3.4. To compare prognostic understanding in patients assigned to stepped PC versus early integrated PC.
- 7.3.5. To compare depression in patients assigned to stepped PC versus early integrated PC.
- 7.3.6. To compare health care utilization at the end of life (i.e., emergency department visits, hospitalizations, and chemotherapy administration) in patients assigned to stepped PC versus early integrated PC.

7.4. Sample Size and Power Calculation

The primary endpoint of the study is to establish that stepped PC is non-inferior to early integrated PC in the change in QOL, as measured by the FACT-L at week-24. Although the primary endpoints in our previous studies assessed the change in FACT-L from baseline to week-12, we chose to focus on QOL at 24 weeks as the life-expectancy of patients with advanced lung cancer has improved over the last few years. Thus, examining QOL at 12 weeks may overlook important differences between groups as the disease progresses. In our most recent trial of early integrated PC versus standard oncology care, we observed a 7.5-point difference in the FACT-L at week-24 favoring the integrated PC group. Thus, we chose a conservative non-inferiority margin of 4.5 points, which is slightly less than 50% of the previously observed advantage with early integrated PC compared to oncology care alone. As a 6-point difference in FACT-L score is considered the lowest range of a clinically meaningful difference, our non-inferiority margin would not reach the threshold of clinically meaningful difference in QOL.⁵⁵ With

188 patients per group, we will have >80% power to establish the non-inferiority of stepped PC compared to early integrated PC on the FACT-L with a one-sided alpha of 0.05, and a non-inferiority margin of 4.5 points. We are currently observing 35% missing data across sites at 24 weeks, primarily due to progressive illness or death. Therefore, we increased our sample size to 255 per group to ensure we have adequate power to assess for non-inferiority of stepped PC.

Our study also has adequate power to assess for non-inferiority of stepped PC compared to early integrated PC in EOL communication and hospice length-of-stay. With a sample size of 510, we will have >80% power, with a one-sided alpha of 0.05, to reject the hypothesis that patient-reported EOL communication with stepped PC would be 10% lower than early integrated PC, assuming that the rate of EOL communication in the early integrated PC group is 30% (based on our recent trial). With this sample size, we will also have >80% power to establish the non-inferiority of stepped PC compared to early integrated PC in hospice length-of-stay with a one-sided alpha of 0.05, and a non-inferiority margin of 7 days. We were conservative with our power estimations by using the highest observed standard deviation for all outcomes from prior studies.

Multiple testing: Testing of secondary outcomes will be one-sided for outcomes being tested for non-inferiority and two-sided for outcomes being tested for superiority. The Benjamini-Hochberg false discovery rate (FDR) control approach will be used to interpret results of significance tests of secondary outcomes with an FDR of 0.15. We selected an FDR of 0.15, which denotes the acceptable percentage of results that potentially represent false positives. Analyses of exploratory outcomes will not be adjusted for multiple comparisons, and presented results will emphasize estimates and confidence intervals.

